#### 7.4.4 Reporting Procedures

**Process for identifying AEs, SAEs, and UPs:** Members of the research team who have not already received training in how to recognize and report an adverse event will be trained immediately once the pilot is awarded. The process of recognizing, collecting, and reporting these data will also be explained to all team members with access to the PLWD and their care partners during the study. Reports will be made using the NIA-approved adverse event reporting form. Site investigators will review study data regularly to ensure no adverse events have occurred.

#### Reporting schedule:

If a serious adverse event occurs, clinic staff and investigators will be instructed to report the event to the PI who will notify the IRB and the NIA per the schedule below. The PI will provide a safety report describing the adverse event and any actions taken. The PI will keep a log of all adverse events (minor and serious) in compliance with IRB and NIH policies including whether the event is unrelated, possibly related, or probably related to the study or intervention. This log will be provided to all necessary parties as indicated below.

- All **adverse events that are serious (SAE) and unexpected** (i.e., have not been previously reported for the study's intervention) will be reported to the IMPACT Collaboratory Regulatory and Data Team Leader ([name]), NIA IMPACT Collaboratory Program Officer (PO) ([name]), and the IMPACT Collaboratory DSMB Chair or Safety Officer within 48 hours of the study's knowledge of the SAE.
  - Only those adverse events that are serious (SAE), unexpected, ***and related to the intervention*** must also be reported to Advarra IRB. Unexpected and ***unrelated*** SAEs will be reported to Advarra IRB on a case-by-case basis if requested by the IMPACT Collaboratory DSMB Chair, Safety Officer, or NIA IMPACT Collaboratory PO.
- All deaths will be reported to IMPACT Collaboratory Regulatory and Data Team Leader ([name]), NIA IMPACT Collaboratory PO ([name]), and the IMPACT Collaboratory DSMB Chair or Safety Officer within 24 hours of the knowledge of death.
  - Advarra IRB does not require the specific reporting of death outside of the SAE reporting requirement above, but they will be notified on a case-by-case basis if requested by the IMPACT Collaboratory Chair, Safety Officer or NIA IMPACT Collaboratory PO.
- All **unanticipated problems (UPs)** will be reported to the IMPACT Collaboratory Regulatory and Data Team Leader ([name]), Advarra IRB, NIA IMPACT Collaboratory PO ([name]), and the IMPACT Collaboratory DSMB Chair or Safety Officer within 48 hours of the study's knowledge of the event.
- The summaries of all previously reported unexpected and related SAEs, deaths, and UPs, *as well as* all other SAEs and AEs will be reported to IMPACT Collaboratory Regulatory and Data Team Lead ([name]), Advarra IRB, NIA IMPACT Collaboratory PO ([name]), and the IMPACT Collaboratory DSMB Chair or Safety Officer at a minimum every 6 months, or at a frequency requested by the IMPACT Collaboratory DSMB Chair or NIA IMPACT Collaboratory PO.

Summary table of reporting structure, individuals, and timing.

Reported To	SAE and unexpected A	Deaths B	Unanticipated problems C	Summaries A, B, & C
[name] 	X	X	X	X
[name] 	X	X	X	X
DSMB Chair	X	X	X	X
IMPACT Safety Officer	X	X	X	X
Advarra IRB	X 	X 	X	X
Timing	Within 48 hours	Within 24 hours	Within 48 hours	Every 6 months

 IMPACT Regulatory and Data Team Lead

 IMPACT Collaboratory PO

 Only if also related to intervention

## 7.5 Safety Monitoring

Per the NIA Guidelines on Data and Safety Monitoring, we have an NIA-appointed Data and Safety Monitoring Board and IMPACT Safety Officer (SO). The PI will be responsible for ensuring participants' safety on a daily basis. In addition, the NIA IMPACT Collaboratory DSMB and Safety Officer will oversee all data and safety monitoring activities for this study. The number of DSMB members will be determined by NIA, and one will be designated the Chairperson. DSMB members and the Safety Officer will be appointed by the NIA Director. This DSMB and SO will act in an advisory capacity to the NIA Director and the PI to monitor participant safety, to evaluate the progress of the study, and to review procedures for maintaining the confidentiality of data, the quality of data collection, management, and analyses.

## 7.6 Frequency of Data and Safety Monitoring

The study PI will teleconference into the DSMB meeting to present their safety reports at the intervals described below.

For the study, the frequency of DSM will proceed as follows: 1. Prior to the start of participant enrollment and data collection, the study PI will submit a DSMP for approval by the DSMB and/or the NIA PO; 2. Six months after the initiation of participant enrollment and/or data collection, the study PI will submit a DSM report to the DSMB or Safety Officer. This interim report will be reviewed by the DSMB or Safety Officer to determine whether there are any human subjects or data safety concerns; and 3. At the end of the study, the PI must submit a final DSM report to the DSMB and Safety Officer.

## 7.7 Content of Data and Safety Monitoring Report

The content of the data and safety monitoring report will include:

- Name of the organization conducting the research
- Title of the research project
- Name of the principal investigator on the protocol
- Number of the research project assigned by the Advarra IRB
- Study status

- Participants screened, enrolled, completed, and discontinued
- Participant risk vs. benefit
- Performance of study sites
- Safety information
  - Detailed description of any adverse or serious adverse events
  - Actions taken or planned to address identified issues/problems
- Study quality
  - Data quality and timeliness of data collection
  - Fidelity of intervention based on measures of completeness of intervention components

For any reportable incidents, the local site study team, including the MCC, will unmask the study subject as required to share with the DSMB.

## 7.8 Conflict of Interest for DSMB Members

Each DSMB member and the Safety Officer will sign a [\*\*Conflict of Interest Statement\*\*](#) which includes current affiliations, if any, with pharmaceutical and biotechnology companies (e.g., stockholder, consultant), and any other relationship that could be perceived as a conflict of interest related to the study and / or associated with commercial interests pertinent to study objectives.

## 7.9 Protection of Confidentiality

Data will be presented in a blinded manner during the open sessions of the DSMB. At DSMB meetings or in reports, data and discussion are confidential. Participant identities will not be known to the DSMB members.

## 8 **INTERVENTION DISCONTINUATION**

The intervention may be voluntarily discontinued by a subject at any time. In addition, if a subject is permanently transferred from their home to a long-term care facility, they will no longer be eligible to continue the study. There are no other reasons to discontinue a subject from the intervention as long as they continue to live at home, have an informal care partner, and are willing to participate.

We will continue to collect data on subjects who withdraw voluntarily from participation in the study. All data collection is passive, pulled from the EHR where the subject receives their regular primary care.

Subjects who discontinue before the study has completed will be replaced, if possible, as long as this does not extend the length of the study.

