# 6 STUDY PROCEDURES

All outcomes' data will be collected from the participating HCOs' respective EHRs using existing data regularly collected to provide standard patient care and to monitor quality. Participants enrolled in the

intervention will be ‘flagged’ in the EHR as pilot participants and monitored longitudinally.

AMGA regularly collects data from HCOs on a monthly or quarterly basis for all quality improvement, research, and best practices learning collaborative programs, and has a long history of creating detailed data specifications and reporting templates to which member organizations respond and complete. Participating sites have confirmed their ability to do this for this pilot. Monthly data will be submitted to AMGA at the end of study months three, seven, and 10 (see milestones and timeline). Seven total months of EHR data will be collected from each participant: three months prior to enrollment, three months during the intervention, and one month post program discharge.

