## 6.1 Summary of primary and secondary outcome measures by data collection interval relative to patient enrollment

Outcome Measure	Study Month -3	Study Month -2	Study Month -1	Baseline/ Enrollment Study Month 0	Study Month 1	Study Month 2	Study Month 3	Post Study Month 4
Hospital Transfers (hospitalizations, ED visits, observation stays)	X	X	X		X	X	X	X
Number of Medications	X	X	X		X	X	X	X
Number of Anti-psychotics Rx	X	X	X		X	X	X	X
Number of acetylcholinesterase inhibitors Rx	X	X	X		X	X	X	X
Number of memantine Rx	X	X	X		X	X	X	X
Sex				X				
Age				X				
Race				X				
Ethnicity				X				
Rural Residence				X				
Comorbidities				X				

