### 9.4.1 Primary outcome

The primary outcome is hospital transfers (hospitalizations, emergency department visits, observation stays without admission), and will be collected on each enrolled patient over a 7-month period. Per the table above, data will be collected monthly for the 3 months prior to enrollment, the 3 months during enrollment, and one month post enrollment.

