### 9.4.2 Secondary outcomes

The secondary outcomes are number of total medications, number of anti-psychotics, acetylcholinesterase inhibitors, and memantine medications and will be collected on each enrolled patient over a 7-month period. Per the table above, data will be collected monthly for the 3 months prior to enrollment, the 3 months during enrollment, and one month post enrollment.

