## 9.5 Data Analyses

A total of 150 PLWD and their care partners receiving care at one of three primary care practices at two health care organizations will be enrolled in the intervention to maximize the likelihood that this pilot study will support the feasibility, generalizability, and scalability to a full-scale ePCT. Data on an additional 100 patients will be extracted for data validation. Data collected during the pilot study will help inform the full ePCT by testing implementation and data collection procedures. Because patients will be enrolled on a rolling basis, we will establish the measurement periods individually for each patient, e.g., for the primary outcome of hospital transfers, we will measure the number of monthly hospitalizations over a 7-month period: three months prior to enrollment, three months during, and one month post discharge from the program. This will allow us to compare the baseline rate (rate of hospitalizations per 1,000 person-days prior to enrollment) with the hospitalization rate in the three months while the patient is enrolled. We will also collect data from the month following program discharge to assess whether hospitalization rates are maintained. We will follow a similar strategy for the secondary outcome of total number of active medications per month. Only exploratory analysis will be performed on the pilot data due to lack of a comparison/control population and low sample size. Descriptive statistics of the study population characteristics and outcomes will be calculated, including stratification at both the cluster and demographic level to identify potential disparities. Outcomes will be compared between the pre- and post-intervention time periods to estimate the effect size of the intervention and will be evaluated using repeated measures ANOVA, though the sample size of the pilot study may not permit definitive results. The R programming language will be used to carry out analysis. Survey results will be reported using descriptive statistics (means and standard deviations for continuous variables and frequency percent for discrete variables) to summarize individual survey items along with histograms for distributions of variables and bar charts/other charts to present the data. To plan for the full trial, we will conduct exploratory analysis to determine measurement reliability and the rate of missingness of patient level (baseline outcome rates, age, sex, race/ethnicity, and comorbidities) and cluster level covariates.

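### Do patients who move to long-term care drop out of the EHR outcome data, leaving the person-day rate without a proper denominator?

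*Combined protocol and SAP*

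**What the plan says.** Section 8 names two ways of leaving: voluntary discontinuation, and a permanent move. On the second it says that "if a subject is permanently transferred from their home to a long-term care facility, they will no longer be eligible to continue the study". The next paragraph states "We will continue to collect data on subjects who withdraw voluntarily from participation in the study", followed by the general remark "All data collection is passive, pulled from the EHR where the subject receives their regular primary care". Movers are not mentioned there.

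The follow-up rule is stated several times without exception. Section 6: "Seven total months of EHR data will be collected from each participant". Section 9.4.1 says the primary outcome "will be collected on each enrolled patient over a 7-month period". Section 9.4.2 repeats this for the medication counts, and Sections 6.2 and 10.1 agree.

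Section 10.1 expresses the primary outcome as transfers per 1,000 person-days. Section 9.5 compares the baseline rate on that scale "with the hospitalization rate in the three months while the patient is enrolled". The table in Section 6.1 lists monthly items, beginning with "Hospital Transfers (hospitalizations, ED visits, observation stays", plus baseline characteristics. It shows no days-observed item. Section 11.3.1.1 says event dates are not needed.

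**The concern.** Two things look wrong.

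First, continued collection is spelled out for one kind of leaver and not for the other. A reader could infer that movers' data end at the move, and the phrase in Section 9.5 about time while enrolled could be taken the same way. A move to long-term care is plausibly linked to hospital use. Losing the time after it would remove higher-risk person-time from the during and post periods but not from the baseline, and so flatter the program. Section 9.5 names no outcome analysis set that would rule this out.

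Second, a rate per person-day needs days at risk. If the extract holds only monthly counts, someone who dies or leaves mid-month could be credited with days on which no event could be seen. That error also falls on the during-program side and favors the program. At stake is the exploratory effect-size estimate and, more broadly, Aim 3, which tests whether outcomes can be ascertained over time from the EHR.

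**Working it through.** **The plan's own model.** Section 9.2 uses a base rate of 0.50 transfers per 3 months, a 25% reduction (to 0.375) and reports 37.5% power. With n = 150 per period, the square-root Z-test and two-sided 0.05 (assumed, since alpha is not stated): Φ(|√0.50 − √0.375| / √(2/600) − 1.96) = Φ(0.0947/0.0577 − 1.96) = 37.5%. It reproduces, so m = 0.50 and n = 150 are used below.

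**How many patients.** The documents give no move rate for this pilot. Section 2.2 gives mean times to long-term care or death of 470 and 506 days over 18 months (548 days). Assuming a constant hazard h, (1 − exp(−548h))/h = 470 or 506 gives h = 0.000575 or 0.000295 per day. Over 91.3 days this is 5.1% or 2.7%, or 7.7 or 4.0 of 150. Deaths are included, so moves alone are fewer.

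**If data stopped at the move.** Assumptions: a share p of 2–5% move at mid-period; movers have e = 0.5–1.0 extra transfers per 3 months in both periods; there is no true effect. Baseline = m + pe. Events before the move: E = (1 − p)m + 0.5p(m + e). The ratio with actual days is [E/(1 − 0.5p)]/(m + pe). The ratio with full calendar days but later events missed is E/(m + pe).

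| p | e | m + pe | E | actual days | calendar days |
|---|---|---|---|---|---|
| 0.02 | 0.5 | 0.510 | 0.5000 | 0.990 | 0.980 |
| 0.02 | 1.0 | 0.520 | 0.5050 | 0.981 | 0.971 |
| 0.05 | 0.5 | 0.525 | 0.5000 | 0.977 | 0.952 |
| 0.05 | 1.0 | 0.550 | 0.5125 | 0.956 | 0.932 |

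Following everyone, as the seven-month rule provides, gives 1.00.

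If the excess falls only just before the move and is absent at baseline (p = 0.05, e = 1), stopping at the move gives [(0.95 × 0.50 + 0.05 × (0.25 + 1))/0.975]/0.50 = 1.103. Full follow-up gives 1 + 0.05/0.50 = 1.100. Stopping then hardly matters.

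**Denominator alone.** Take no excess risk in leavers, an exit share q by day 90, counts cut at exit, and 90 days credited to all. The observed fraction is (1 − exp(−90λ))/(90λ) with λ = −ln(1 − q)/90. For q = 2.5% it is 0.987 and for q = 5% it is 0.975, so the spurious reduction is 1.3% or 2.5%. A true 25% reduction would read as 25.9% or 26.9%. If the exit month is known and only that month's days are unresolved, 4 to 8 patients × 30.4 / (150 × 91.3) = 0.9% to 1.8% of person-days.

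**Against sampling error.** 150 × 0.50 = 75 transfers per period. Treating the periods as independent Poisson counts, exp(±1.96√(2/75)) = 0.73 to 1.38.

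**The case for a change.** The best case for acting is that the pilot exists to try out data procedures for a larger trial. Section 9.2 plans 12 months there with the same outcome. Carrying the Section 2.2 hazards forward, 1 − exp(−365h) gives about 10–19% reaching long-term care or death. The lost person-time, 1 − (1 − exp(−365h))/(365h), is about 5–10% if observation ended at that point. Two health systems extract the data and could read Section 8 differently. One sentence and a site-computed day count would be cheap and would send out no dates.

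Part of this stands. Section 8 is silent on movers, no person-day definition is written down, and the matter will carry more weight in the full trial. It does not show that this pilot's plan gives a wrong answer. Section 8 concerns leaving the intervention, and its remark on passive collection covers all data. The Section 6.1 table is headed as a summary of measures, and Section 6 refers to fuller data specifications that are not in the documents, so a days count is unmentioned and not shown to be absent. Section 10.1 provides a test dataset after month one and chart review of ascertainment. Section 4.3 has coordinators record retention and loss, Section 6.2.2 records the enrollment date, and Section 7.4.4 requires prompt reporting of deaths.

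A column for days under EHR capture is also harder to define than it sounds. Section 3.2 typically counts as active anyone with any service in three years, so nearly every day after a move would qualify and the column would miss the lost capture it was meant to find.

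**Conclusion.** No change follows. The ordinary reading is that a mover leaves the program while the passive extract runs its seven months, and under that reading, with full capture, the illustrated bias is zero. How person-days are counted for the few patients who die or leave capture is a detail that the analyst and sites can settle with the data specification and test dataset.

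On the adverse reading the shift is 1–4% with actual days, and 2–7% with calendar days and missed events, against an interval of roughly 27% below to 38% above. Sections 9.1 and 9.5 say there is no hypothesis and only exploratory analysis.

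This rests on assumed move rates and assumed excess transfers in movers, since the documents give neither. It also rests on a constant hazard behind the 4 to 8 exits, and on independent Poisson counts for the interval. Loss of EHR capture after a move is possible, but it is one of the things Aim 3 sets out to learn.

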## 9 **STATISTICAL CONSIDERATIONS**

### 9.1 General Design Issues

We expect to include a total of 250 patients in the pilot study. Of these, 100 patients will serve as a data validation arm to demonstrate the feasibility of collecting and validating data from large health systems and will not be enrolled in the intervention. The pilot study is intended to test the feasibility of integrating the intervention (MIND at Home) into primary care, as well as the processes and procedures of identifying and recruiting subjects and collecting data. Therefore, we do not have a statistical hypothesis because the pilot study is not powered to demonstrate statistically significant results.

## 9.2 Sample Size and Randomization

The pilot study is not powered to detect significant changes in our selected outcome measures. However, we estimated power, nonetheless. Preliminary studies of the MIND at Home program report a reduction from 1 to 0.73 in number of hospital admissions per year, or a 27% decrease. Our primary outcome is hospital transfers (which includes admissions but also ER visits and observation stays without admissions), but we expect that the relative effect size on this outcome will be similar to hospital admissions alone. Because our observation periods are 3 months (as opposed to 1 year), our assumed base rate is 0.50. To make our power estimates slightly conservative, we will assume an effect size of 25%. Given these factors, the estimated power is 37.5% to detect the effect (Z-test with square root adjustment for low base rates). This low power is primarily caused by the short duration of the intervention per patient in the pilot, making outcome observations (transfers) very rare. In the full trial we will use a 12-month intervention period.

For the full trial, sample size estimates will be based on the primary outcome (hospital transfer rate over 12 months). We intend to implement a cluster-controlled cohort design with a baseline period, which requires specialized power calculations (Hemming et al., 2020). Calculations will assume a Poisson distribution of hospitalization rates, equal cluster sizes, and an equal number of clusters in the treatment and control arms. Because validated estimates of correlations are not available, we will use conservative assumptions for intra-cluster correlation (0.05) and individual autocorrelation (0.2). Baseline hospital transfers are estimated to occur at a rate of 1 transfer per year. Assuming this rate, the study will be powered to detect a 0.2 absolute reduction (20% relative reduction) at greater than an 80% power level. This will require at least 11 clusters in each arm of two study arms, with each practice recruiting approximately 50 patients. Analysis of the full study will make use of mixed-model ANCOVA, controlling for both patient level and cluster level confounding variables.

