- ***Reductions in use of acute and institutional care and total spending.*** MIND Pilot and MIND-HCIA showed health care utilization patterns and spending redistribution away from acute/institutional care, towards home-, community- and physician-based services. A sub analyses in MIND-HCIA showed a reduction in total Medicaid spending and slower growth in Medicaid inpatient spending and LTC spending compared to propensity matched controls. A pre-post Poisson regression analyses of a pooled sample of MIND intervention recipients (MIND HCIA+MIND RCT; n=442) showed mean number of hospital admissions decreased by 27% (1-0.73) within one year after baseline (95% CI: 6%, 44%, p=0.01). Rates of ≥1 hospitalization declined 36.8% to 32.5%, a crude rate pre/post reduction of 11.6% (unadjusted).
- ***Improvement in care quality, behavior, and high program satisfaction.*** MIND is associated with decreases in unmet care needs on the JHDCNA, improved quality of life, and reduced time spent with the PLWD (objective caregiver burden)(unadjusted) compared to augmented usual care in RCT. In the MIND HCIA, MIND recipients had fewer overall unmet dementia-related needs (PLWD:  $\beta$ =-19.95, SE 0.7, p<0.0001) and in all subdomains (all p<0.0007), fewer behavioral issues (NPI) ( $\beta$  = -5.16, SE 1.4, p=0.0003), reduced caregiver burden (ZBI short) ( $\beta$  = -1.69, SE 0.6, p=0.0054), and reduced caregiver distress (NPI-Distress) ( $\beta$  = -1.63, SE 0.8, p=0.0347) from baseline to 18 months (within subject, pre-post adjusted mixed models). Program satisfaction data (n=390) show that recipients had high service in all domains.
- ***MIND at Home is potentially cost-effective.*** In MIND-HCIA, cost for delivery of MIND were estimated. A difference-in-differences analysis of Medicaid spending estimated return-on-investment (ROI) for a subgroup of participants with claims data (120 dually eligible MIND participants vs. 360 matched controls). The average cost to deliver MIND per enrollee per month was \$110, or \$1,320 per annum. Medicaid expenditures of dual eligibles grew 1.12 percentage points per quarter more slowly than matched controls. Savings came from slower growth in

inpatient and LTC use. The five-year Medicaid savings were estimated at \$7,052 per beneficiary, a 1.12-fold ROI.

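### Section 9.2 presents a 27% relative fall in admissions as a drop between two annual rates that Section 2.2 does not report; separately, the 0.50 base rate behind the 37.5% power is unsourced and conflicts with the section's own 1 per year

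*Combined protocol and SAP*

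**What the plan says.** Section 2.2 (Study Rationale) describes the source as "A pre-post Poisson regression analyses of a pooled sample of MIND intervention recipients (MIND HCIA+MIND RCT; n=442") and reports that it "showed mean number of hospital admissions decreased by 27% (1-0.73) within one year after baseline (95% CI: 6%, 44%, p=0.01"). The only absolute figures beside it are the shares of patients with any admission: "hospitalization declined 36.8% to 32.5%, a crude rate pre/post reduction of 11.6% (unadjusted"). No mean number of admissions per patient appears.

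Section 9.2 (Sample Size and Randomization) restates this as earlier studies that "report a reduction from 1 to 0.73 in number of hospital admissions per year, or a 27% decrease". It expects the relative effect on transfers (admissions, emergency visits and observation stays) to resemble the effect on admissions. It then sets the pilot base rate: "Because our observation periods are 3 months (as opposed to 1 year), our assumed base rate is 0.50". It takes 25% as the effect and states power of 37.5% from a Z-test with a square-root adjustment.

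For the full trial, the same section assumes a baseline of 1 transfer per year and an absolute reduction of 0.2, leading to at least 11 clusters per arm with about 50 patients each.

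**The concern.** There are two faults, and they are independent.

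First, a relative effect seems to have been rewritten as a pair of observed annual rates. A reader of Section 9.2 alone would believe that earlier MIND cohorts averaged 1 admission per patient-year. Section 2.2 does not show that.

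Second, the base rate that enters the power calculation is neither of those numbers. The only reason given for 0.50 is the move from 12 months to 3 months, but that move applied to 1 per year gives 0.25. The full trial's rate for the same transfer outcome, 1 per year, also prorates to 0.25. Section 9.2 therefore carries two transfer rates that differ by a factor of two and explains neither.

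The Précis and Section 1.1 name sample-size data for the future trial among the pilot's goals. A rate believed to have been observed is likely to be carried forward into that design without challenge.

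**Working it through.** **1. Is 0.73 a ratio or a rate?** Inputs are from Section 2.2.
- 1 − 0.73 = 0.27, so the bracket is the arithmetic for the 27%.
- A CI of 6% to 44% corresponds to ratios of 1 − 0.06 = 0.94 and 1 − 0.44 = 0.56.
- Geometric midpoint: √(0.94 × 0.56) = 0.726. Arithmetic midpoint: 0.75. The interval is centred on 0.73 on the log scale, as a Poisson-regression rate ratio would be.
- SE of the log ratio: ln(0.94/0.56)/(2 × 1.96) = 0.132. Then z = ln(0.73)/0.132 = −2.38 and p ≈ 0.017, broadly in line with the stated 0.01.

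**2. Reproduce the stated power.** Inputs are base rate 0.50 and a 25% fall (Section 9.2) and 150 patients in each period (Section 9.5). Section 9.2 gives no alpha for the pilot, so two-sided 0.05 is an assumption. The periods are treated as independent.

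Power = Φ( 2(√λ₀ − √λ₁)/√(2/150) − 1.96 )

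- λ₀ = 0.50 and λ₁ = 0.375: 2(0.7071 − 0.6124) = 0.1895. Dividing by 0.1155 gives 1.641, and Φ(1.641 − 1.96) = 37.5%. The plan's figure reproduces.

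**3. Does the misquotation move it?** No. The formula takes the relative effect and the base rate of 0.50. A 27% fall is the same whether 0.73 is a ratio or a rate.

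**4. Does 0.50 follow from anything stated?**
- 1 admission per year × 3/12 = 0.25.
- 1 transfer per year (full trial) × 3/12 = 0.25.
- 0.50 per 3 months × 4 = 2 per year, a figure that appears nowhere in the documents.

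**5. Power over the section's own two rates**, 25% fall, same formula:

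| Base rate per 3 months | Per year | Expected transfers before enrollment (150 patients) | Power |
|---|---|---|---|
| 0.25 | 1 | 37.5 | 21.2% |
| 0.50 | 2 | 75 | 37.5% |

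At 0.25: 2(0.5000 − 0.4330) = 0.1340. Dividing by 0.1155 gives 1.160, and Φ(1.160 − 1.96) = 21.2%.

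**6. A caveat on reproduction.** With base rate 0.25 and a before-after correlation of 0.5 within patients, the standard error becomes √(2 × 0.5/150) = 0.0816. The test statistic is again 1.641 and power is again 37.5%. The printed 0.50 could therefore be a mis-stated √0.25. The documents do not settle this, which is a further reason to give the inputs in full.

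**The case against.** Section 2.2 never uses the term rate ratio, and the hyphen in its bracket could mark a range of mean counts. The investigators may hold those counts. That is fair: the reading in step 1 is an inference, although the model, the arithmetic and the shape of the CI all point to it.

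The transfer outcome is wider than admissions, so a rate above 1 per year is plausible. That stands as a possible explanation of 0.50. However, Section 9.2 does not offer it, and the full trial uses the same wider outcome at 1 per year. The section does call both base rates assumed or estimated, so neither is itself passed off as an observed result.

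Section 9.1 states no hypothesis, Section 9.5 limits the pilot to exploratory analysis, and 150 is not derived from this power. A lower figure would only reinforce the plan's own statement that power is low. This stands and limits the weight of the point.

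A reader might also infer a true admission rate from "Rates of ≥1 hospitalization declined 36.8% to 32.5" per cent, since a simple Poisson gives −ln(1 − 0.368) = 0.46 per year, against 63.2% with any admission at a mean of 1. The documents do not support that step:
- The same conversion of the later share gives −ln(1 − 0.325) = 0.393, a ratio of 0.86 rather than 0.73 (adjustment may explain part of the gap).
- With n = 442 and independent Poisson counts, the reported CI would need a mean near (1 + 1/0.73)/(442 × 0.132²) = 0.31. That is below 0.368, the least the mean can be when 36.8% have at least one admission.

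The earlier counts are thus not simple Poisson. With overdispersion a mean of 1 remains possible, at 1/0.368 = 2.7 admissions per hospitalized patient.

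**Conclusion.** Section 9.2 is wrong as written on two counts. It attributes absolute annual admission rates to earlier work that, as summarised in Section 2.2, reports only a relative reduction. It also rests the pilot power on a base rate that is unsourced, does not follow from the reason given, and is twice the rate assumed for the full trial once both are put on one time scale. Using the section's 1 per year in place of 0.50 per 3 months takes the stated power from 37.5% to about 21%, assuming two-sided 0.05, 150 per period and independent Poisson counts.

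Two stronger conclusions are tempting and do not hold. One is that the misquotation produced the 37.5%; step 3 shows that it did not. The other is that the plan misdescribes its effect size in saying "To make our power estimates slightly conservative, we will assume an effect size of 25" per cent. By the same formula, power at base rate 0.50 is 43.0% for a 27% fall and 37.5% for 25%, so the description is fair relative to the point estimate.

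The consequence for the pilot is modest. The main risk is that an annual rate believed to have been observed is carried into full-trial planning.

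**What to change.** - Replace the source sentence in Section 9.2 with a statement that earlier uncontrolled pre-post work found a 27% relative reduction in admissions (rate ratio 0.73, 95% CI 0.56 to 0.94). If the investigators hold the actual mean counts before and after, quote those in both Section 2.2 and Section 9.2.
- State that 0.50 transfers per 3 months and 1 transfer per year are both assumptions. Reconcile them, or explain why the pilot and full-trial populations or definitions differ.
- Give the alpha, sidedness, number per period and any within-patient correlation used for the pilot power, and restate it over the range: about 21% at 0.25 and 37.5% at 0.50 for a 25% fall.

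The cost is a few sentences and a rerun of a one-line calculation. Enrollment, data collection and analysis do not change. The stated power becomes a range with a lower bottom end.
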